4. DATA HANDLING DEFINITIONS AND CONVENTIONS

4.1. Scheduled Study Evaluations and Study Periods

4.1.1. Day 1

Day 1 is the date that the first application of ruxolitinib cream or vehicle cream is administered to the participants in the specific period.

For randomized participants not treated with any study drug, Day 1 is defined as the date of randomization.

4.1.2. Study Day

If a visit/reporting date is on or after Day 1, then the study day at the visit/reporting date will be calculated as

```
Day \# = (visit/reporting date - Day 1 date + 1).
```

If the visit/reporting date is before Day 1, then the study day at the visit/reporting date will be calculated as

```
\text{Day } \# = (\text{visit/reporting date} - \text{Day 1 date}).
```

A study day of -1 indicates 1 day before Day 1.

4.1.3. Baseline Value

Baseline is the last nonmissing measurement obtained before or on the day of the first application of ruxolitinib cream or vehicle cream for the DBVC period.

For randomized participants not treated with any study treatment, baseline is defined as the last nonmissing assessment before or on the date of randomization.

For participants who continue in the OLE period, baseline is defined as follows:

- For efficacy evaluation in the OLE period, baseline is the last nonmissing measurement obtained before or on the day of first application of study treatment in the DBVC period.
- For safety evaluation in the OLE period, baseline is the last nonmissing measurement obtained before or on the day of first application of ruxolitinib 1.5% cream in the study.

When a scheduled assessment and an unscheduled assessment occur on the same day and the times of the assessments are not available, use the following convention to determine baseline:

- If both a scheduled and an unscheduled visit are available on the day of the first application and the time is missing, use the scheduled assessment as baseline.
- If the scheduled assessment is missing on the day of the first application and an unscheduled assessment is available, use the unscheduled assessment as baseline.

4.1.4. Handling of Missing and Incomplete Dates

In general, values for missing dates will not be handled unless methods for handling missing dates are specified in this section or relevant sections. The original reported dates collected on the eCRF should be used in all relevant listings. The following rules will be used for handling partial dates for analyses requiring dates.

Partial LS diagnosis date will be handled as follows in the calculation:

- If only the day is missing, then the fifteenth of the month will be used.
- If both the month and day are missing, then 01 JUL of the year will be used.
- If the diagnosis date is completely missing, then the time since diagnosis will not be calculated.

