5.1. Inclusion Criteria

Participants are eligible to be included in the study only if all of the following criteria apply:

- 1. Ability to comprehend and willingness to sign a written ICF for the study.
- 2. Females only, aged 18 years or older at screening.
- 3. Biopsy-proven LS in the anogenital area. Total BSA including anogenital and nonanogenital area should not exceed 10% BSA.
 - *Note:* Participants who have newly diagnosed LS, or have LS refractory to prior treatments, or have progressive LS (such as fusion of the labia minora, phimosis of the clitoral hood, and fissures) will be allowed to participate in the study.
- 4. Baseline IGA score > 2 for LS.
- 5. Baseline Itch NRS score ≥ 4 in anogenital area. Baseline Itch NRS score is defined as 7-day average of Itch NRS score before Day 1 (data from a minimum 4 out of 7 days directly prior to Day 1 is needed).

- 6. Participants who agree to discontinue all agents used by the participant to treat LS from the screening visit (according to washout timeline enumerated under exclusion criterion 4; see Section 5.2) through the final safety follow-up visit.
- 7. Willingness to avoid pregnancy based on the criteria below.
 - a. Female participants who are WOCBP must have a negative serum pregnancy test at screening and a negative urine pregnancy test before the first application on Day 1 and must agree to take appropriate precautions to avoid pregnancy from screening through 30 days (1 menstrual cycle) after the last application of study treatment and must refrain from donating oocytes during this period. Permitted methods in preventing pregnancy (see Appendix A) should be communicated to the participants and their understanding confirmed.
 - b. A female participant not considered to be of childbearing potential as defined in Appendix A is eligible.

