8.5.3. Biopsy

A biopsy can be performed at screening to confirm LS diagnosis if no previous biopsy was done to confirm the diagnosis and to rule out other diagnoses. If a biopsy is done to confirm the diagnosis of LS, the screening period can be extended to 6 weeks to allow for histological examination. (The diagnostic biopsy is evaluated locally.)

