6.1.3. Disease History

The time since disease duration will be summarized for all participants in the ITT population.

Time since diagnosis (ie, disease duration [years]) will be calculated as follows:

Disease duration (years) = (date of randomization – date of initial LS diagnosis +1) / 365.25

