9.2. Adverse Events

9.2.1. Adverse Event Definitions

A TEAE is any AE either reported for the first time or worsening of a pre-existing event after first application of study drug until 30 days of the last application of study drug. For participants who cross over treatments, the first application date is period-specific; however, the end date is 30 days after the last application date in this period, or the first application date in the next period, whichever comes first. Analysis of AEs (as discussed below) will be limited to TEAEs, but data listings will include all AEs regardless of their timing in relation to study drug application. For purposes of analysis, all AEs will be considered TEAEs unless the AE can unequivocally be defined as not treatment-emergent.

Adverse events will be tabulated by MedDRA PT and SOC. Severity of AEs will be graded using the NCI CTCAE v5. The CTCAE reporting guidelines and grading details are available on the Cancer Therapy Evaluation Program website.

The subset of AEs considered by the investigator to be related to study drug will be considered to be treatment-related AEs. If the investigator does not specify the relationship of the AE to study drug, the AE will be considered to be treatment-related. The incidence of AEs and treatment-related AEs will be tabulated. In addition, serious TEAEs will also be tabulated.

Any missing onset date, causality, or severity must be queried for resolution. Unresolved missing causality and severity will be handled according to the following rules:

- An unresolved missing causality will be considered treatment-related.
- An unresolved missing severity will be identified as an unknown severity.

Any missing onset date of a TEAE will be handled according the following rules:

- If completely missing, then Day 1 will be used.
- If only the day is missing, then the first day of the month or Day 1, whichever is later, will be used.
- If both the month and day are missing, then 01 JAN of the year or Day 1, whichever is later, will be used.

For purposes of analysis, all AEs will be considered TEAEs unless the AE can unequivocally be defined as not treatment-emergent.

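### Partial LS diagnosis dates are imputed without a cap at randomization, so a recently diagnosed woman can be given a zero or negative disease duration; the harm is confined to one descriptive baseline row

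*SAP*

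**What the plan says.** SAP section 4.1.4 gives three rules for LS diagnosis dates:

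- Day missing: "If only the day is missing, then the fifteenth of the month will be used".
- Month and day missing: "If both the month and day are missing, then 01 JUL of the year will be used".
- Whole date missing: "If the diagnosis date is completely missing, then the time since diagnosis will not be calculated".

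SAP section 6.1.3 then derives "Disease duration (years) = (date of randomization – date of initial LS diagnosis +1) / 365.25". The result is a baseline disease characteristic (section 6.1.2; Tables 1.3.1 and 1.3.2 in Appendix A). It also defines a subgroup for the primary endpoint, cut at 1 and 5 (section 7.3.2).

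The note to inclusion criterion 3 in Protocol section 5.1 names, among those who may enter, "Participants who have newly diagnosed LS, or have LS refractory to prior treatments". Protocol section 8.5.3 adds: "A biopsy can be performed at screening to confirm LS diagnosis if no previous biopsy was done". In that case "the screening period can be extended to 6 weeks to allow for histological examination". Neither document puts an upper limit on an imputed diagnosis date or a floor on the duration.

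**The concern.** A woman whose LS was diagnosed shortly before entry can have her diagnosis in the same calendar month or year as her randomization. If her record then lacks the day, or the day and month, the fixed imputed date may fall after randomization. The duration formula would report that she was randomized before she had the disease.

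What is at stake is the credibility of one reported baseline row. An impossible minimum would show in the table. Correcting it at that stage means either departing from the SAP after the fact or relying on an unwritten programming convention that a second programmer need not reproduce.

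**Working it through.** The plan states no figure on this point, so there is nothing to reproduce. The check applies the SAP's own rules to every randomization date in one ordinary year (2023) and one leap year (2024).

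**Inputs.** Imputed day 15 or 01 JUL (SAP 4.1.4); duration = (randomization - diagnosis + 1)/365.25 (SAP 6.1.3); about 60 women randomized 1:1, so about 30 per arm (SAP 3.1).

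**Year-only date, diagnosed in the year of randomization**

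- Randomized 1 January 2023: 1 Jan - 1 Jul + 1 = -180 days; -180/365.25 = -0.493 years. In 2024: -181/365.25 = -0.496 years.
- The value stays negative up to randomization on 29 June (180 of 365 dates in 2023; 181 of 366 in 2024) and is exactly 0 on 30 June.
- Example: randomized 10 April 2023 gives -81/365.25 = -0.222 years. If the true diagnosis was 20 February 2023, the correct value is 50/365.25 = 0.137 years.

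**Day missing, diagnosed in the month of randomization**

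- Randomized on the 1st: 1 - 15 + 1 = -13 days; -13/365.25 = -0.036 years.
- Negative for randomization on days 1 to 13 (12 x 13 = 156 dates a year) and exactly 0 on day 14.
- Example: May 2023, randomized 10 May 2023, gives -4/365.25 = -0.011 years.

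**Effect on an arm mean.** The worst year-only case replaces 1 day by -180 days, a difference of 181 days: 181/365.25 = 0.496 years, and 0.496/30 = 0.0165, about 0.017 years (6 days). The worst day-missing case is 14/30 = 0.47 days.

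**Effect on the subgroups.** Every woman given a zero or negative year-only value was randomized by 30 June of her diagnosis year. Her true duration is at most 181 days (182 in a leap year), and 182/365.25 = 0.498 years. The true and the imputed value both fall in the lowest group, reading the cut points in years as in section 6.1.3.

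**With the cap.** Using the earlier of the imputed date and the randomization date, the lowest value is 1/365.25 = 0.0027 years. The April and May examples above both become 0.0027. No duration that is already positive changes.

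**The case against.** The strongest reply is that this may never happen. It needs a partial date that also lies in the month or year of randomization. A diagnosis made at a screening biopsy is the case most likely to carry a full date, since the site performs the procedure and records the diagnosis (Protocol 8.1.5.2). The extremes need diagnosis and randomization both on 1 January, or both on the 1st of a month, so they are arithmetic floors, not expected values. All of this stands. A less extreme negative value needs no such coincidence: a woman diagnosed in February and entered in April, with only the year recorded, is enough.

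Four stronger readings might tempt a reader, and the documents do not support them.

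- *That a sizeable share of participants is affected.* Assume diagnosis uniform over the 1 to 42 days before randomization, and randomization uniform over the year. About 6% of day-missing dates (78/42 x 12/365) and 43% of year-only dates (158.5/365) then come out negative. These shares apply only to women with both a partial date and so recent a diagnosis, and the documents count neither group. Protocol section 2.1 also allows a clinical diagnosis before biopsy, so the initial diagnosis may well precede screening.
- *That efficacy results are distorted.* Duration enters neither the chi-squared test nor the MMRM, and nobody changes subgroup.
- *That listings will show the imputed dates.* Section 4.1.4 keeps the originally reported dates in listings. Whether a derived duration is listed depends on shells held elsewhere.
- *That the SAP contradicts itself because adverse event onset dates are bounded.* Section 9.2.1 does say "If both the month and day are missing, then 01 JAN of the year or Day 1, whichever is later, will be used", but that floor follows from the definition of a treatment-emergent event. It shows that the SAP uses such limits, not that it set one for diagnosis dates and broke it.

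**Conclusion.** The gap is real and minor. As written, sections 4.1.4 and 6.1.3 together can return a zero or negative disease duration for a woman with a partial diagnosis date in the month or year of her randomization. The floor is about -0.04 years with the day missing and about -0.49 years with year only. The visible damage would be an impossible minimum in Tables 1.3.1 and 1.3.2. The shift in the mean is negligible: about 0.017 years for one worst case, assuming about 30 women in the arm. Whether any such date exists cannot be told from the documents. The ITCH4 analysis and the duration subgroups are untouched.

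**What to change.** Add one sentence to SAP section 4.1.4: *if the imputed LS diagnosis date is later than the date of randomization, the date of randomization will be used.* The lowest possible duration is then 1/365.25 years.

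The cost is that sentence and one line of code, with a small downside: the cap assigns the shortest feasible duration. For a year-only date and randomization on 29 June 2023, the true duration can be anything from 1 to 180 days. The present rule gives -1 day and the cap gives 1 day, so the cap repairs the sign but hardly the accuracy. If the sponsor prefers a less biased value, the midpoint between the start of the known month or year and randomization (about 90 days in this example) is acceptable. Either convention will do, provided that it is written down before unblinding.

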4.2. Variable Definitions

4.2.1. Body Mass Index

Body mass index will be calculated as follows:

BMI
$$(kg/m^2) = [weight (kg)] / [height (m)]^2$$

4.2.2. Prior and Concomitant Medication

Prior medication is defined as any nonstudy medication started before the first application of ruxolitinib 1.5% cream or vehicle cream.

Concomitant medication is defined as any nonstudy medication that is started accordingly:

- Before the date of first application of ruxolitinib 1.5% cream or vehicle cream and is ongoing throughout the study or ends on/after the date of first study drug application.
- On/after the date of first application of ruxolitinib 1.5% cream or vehicle cream and is ongoing or ends during the course of study.

A prior medication could also be classified as "both prior and concomitant medication" if the end date is on or after first application of ruxolitinib 1.5% cream or vehicle cream. In the listing, it will be indicated whether a medication is only prior, only concomitant, or both prior and concomitant.

For the purposes of analysis, all medications will be considered concomitant medications unless the medications can unequivocally be defined as not concomitant.

5. STATISTICAL METHODOLOGY

5.1. General Methodology

Unless otherwise noted, SAS® software (SAS Institute Inc, Cary, NC; v9.4 or later) will be used for the generation of all tables, graphs, and statistical analyses. Descriptive summaries for continuous variables will include, but not be limited to the number of observations, mean, standard deviation, median, minimum, and maximum. Descriptive summaries for categorical variables will include the number and percentage of participants in each category.

5.2. Treatment Groups

This is a randomized, DBVC study with an open-label extension period. Table summaries, unless otherwise indicated, will present data by treatment group.

For the DBVC period, the treatment groups will be vehicle cream and ruxolitinib 1.5% cream BID.

For the OLE period, the participants will be grouped into the following groups according to the treatment group they received during the DBVC period:

- Vehicle cream to ruxolitinib 1.5% cream
- Ruxolitinib 1.5% cream

5.3. Analysis Populations

5.3.1. Intent-to-Treat Population

All participants who are randomized will constitute the ITT population. Treatment groups for this population will be defined according to the treatment assignment at the time of randomization regardless of the actual study drug the participant might take during their participation in the DBVC period.

The ITT population will be used for the summary of demographics, baseline characteristics, participant disposition, and analyses of all efficacy data.

5.3.2. Safety Population

The safety population will include all participants who applied ruxolitinib 1.5% cream or vehicle cream at least once. Treatment groups for this population will be determined according to the actual treatment the participant applied on Day 1 regardless of assigned treatment group.

All safety analyses will be conducted using the safety population.

5.3.3. Open-Label Extension Evaluable Population

All analyses for the OLE period will be conducted with the OLE evaluable population, which includes all participants who applied ruxolitinib 1.5% cream at least once during the OLE period.

6. BASELINE, EXPOSURE, AND DISPOSITION

Appendix A provides a list of planned tables, figures, and listings. Sample data displays are included in a separate document.

6.1. Demographics, Baseline Characteristics, and Disease History

6.1.1. Demographics and Baseline Characteristics

The following demographics and baseline characteristics will be summarized by treatment group and overall for the ITT population in the DBVC period and for the OLE evaluable population in the OLE period: age, sex, race, ethnicity, weight, height, and BMI.

6.1.2. Baseline Disease Characteristics

For the ITT and OLE population, the baseline disease characteristics will be summarized by treatment group and will include, but not limited to the following:

- Disease duration (years)
- LS diagnosis confirmed by biopsy (yes/no)
- Anatomic location (vulva/vagina, other anogenital area, other body areas)
- Complications with LS (yes/no)
- Number of flares/episodes of LS in the past year other than current flare
- Clinical manifestations related to LS (% participants with each of the manifestations)
- Prior treatment received for LS (yes/no)
- History of other skin disease (yes/no)
- Family history of LS (yes/no)
- History of skin infection related to LS requiring antibiotic treatment (yes/no)
- Days since onset of current episode of LS flare/activity
- Skin type (Type I/II/III/IV/V/VI)
- Total % BSA affected
- Baseline Itch NRS score
- Baseline total CLISSCO
- Baseline CLISSCO subscores (total score for each section)

- Baseline Skin Pain NRS
- Baseline total LSCA score
- Baseline IGA score

6.1.3. Disease History

The time since disease duration will be summarized for all participants in the ITT population.

Time since diagnosis (ie, disease duration [years]) will be calculated as follows:

Disease duration (years) = (date of randomization – date of initial LS diagnosis +1) / 365.25

6.1.4. Medical History

For participants in the ITT population during the DBVC period, medical history will be summarized by assigned treatment groups. This summary will include the number and percentage of participants with medical history for each body system/organ class as documented on the eCRF.

6.2. Disposition of Participant

The number and percentage of participants who were randomized, treated, and completed the DBVC period, as well as the number and percentage of participants who discontinued the treatment or withdrew from the study during the DBVC period with a primary reason for discontinuation, will be summarized as part of the ITT population.

The number and percentage of participants who completed the OLE period, in addition to those participants who discontinued treatment or withdrew from the study during the OLE period with a primary reason for discontinuation, will be summarized as part of the OLE evaluable population.

6.3. Protocol Deviations

Protocol deviations will be summarized and listed by treatment group and overall ITT and OLE populations.

6.4. Exposure

For participants in the safety population in the DBVC period, the OLE evaluable population in the OLE period, and those who applied ruxolitinib 1.5% cream BID throughout the study, study drug exposure will be summarized by treatment group, descriptively, as follows:

• Duration of treatment (days):

Date of last application of ruxolitinib cream or vehicle cream in the specific period – date of first application of ruxolitinib cream or vehicle cream in the specific period + 1

• Total amount of cream applied (g):

Total weight of ruxolitinib cream or vehicle cream dispensed in the specific period – total weight of ruxolitinib cream or vehicle cream returned in the specific period

• Average daily application:

Total amount of cream applied in the specific period (g) / [duration of treatment with study cream in the specific period (days) – number of interrupted days with study cream in the specific period]

6.5. Study Drug Compliance

The overall compliance (%) for the application of ruxolitinib 1.5% cream BID or vehicle cream BID during the DBVC period will be calculated for all participants in the safety population as follows:

Cream application compliance (%) = $100 \times [\text{total number of nonmissing applications}] / [\text{total number of intended applications}], where$

Total number of nonmissing applications = number of applications that the participants actually applied during the study, and

Total number of intended applications = $2 \times$ duration of treatment (days) – number of interrupted applications.

6.6. Prior and Concomitant Medication

Prior medications and concomitant medications will be coded using the WHO Drug Dictionary. The number and percentage of participants with prior and concomitant medication will be summarized by treatment group, as well as overall for the ITT population during the DBVC period, by WHO drug class and WHO drug preferred term. For the OLE period, only concomitant medications will be summarized based on OLE evaluable population.

7. EFFICACY

Appendix A provides a list of data displays. Sample data displays are included in a separate document.

[figure not shown]
7.1. Efficacy Hypotheses

[figure not shown]
The primary hypothesis is the superiority of ruxolitinib 1.5% cream BID compared with vehicle cream BID in the proportions of participants achieving ITCH4 at Week 12.

7.2. Efficacy Measures

7.2.2. Clinical Lichen Sclerosus Score

The CLISSCO is a validated tool to assess disease severity in vulvar LS. Clinical Lichen Sclerosus Score consists of 12 items divided into 3 sections: symptoms (3 items; likely reversible [ie, itch, pain, dysuria]); signs (3 items; possibly reversible [ie, whitening, petechiae/ecchymosis, fissures]); and architectural changes (6 items; irreversible [ie, skin fusion, perianal involvement, etc]). All symptoms, signs, and architectural changes will be rated on a 4-point Likert scale: 0 (absent), 1 (mild), 2 (moderate), and 3 (severe) (Erni et al 2021). The investigator will be asked to document the score of each of the 12 items; the CLISSCO will be calculated by summing the score of each question with a maximum score of 36 and a minimum score of 0. The higher the score, the more severe the disease. Additionally, the total score for each of the 3 sections (ie, symptoms, signs, and architectural changes) will be summarized by summing the scores of the questions in each section. No imputation will be performed for missing values.

